### 2.5.4 Handling of missing values not related to intercurrent event

If treatment discontinuation prior to Month 18 is due to reasons other than lack of efficacy or death, or if the Month 18 visit was completed but relapse/EDSS/MRI (Gd+ or new/enlarging T2 lesions) was missed at Month 6, 12 or 18, and disease activity was not shown (i.e., MRI activity after Month 6 through 18 or relapse/3-month clinical disability progression between Months 6 and 18), the participant will be excluded from mFAS for all NEDA-3 and associated endpoints efficacy analyses and thusly out of scope for intercurrent events handling.

### 2.5.5 Sensitivity analyses

There are no sensitivity analyses of the primary endpoint planned for this study.

### 2.5.6 Supplementary analyses

The following supplemental analyses of the primary endpoint will be performed:

- An analysis using an observed case approach (completers) using the FAS based on participants who completed their Month 6 and Month 18 visits.

- An analysis using a non-response imputation (NRI) approach using the FAS. NRI will be applied to missing data regardless of intercurrent events. NRI is a conservative imputation method for dichotomous variables. For missing data, the primary endpoint will be imputed as “No”. Refer to [Section 5.1.3.3](#).
- An analysis using the mFAS in which the MRI activity-free component of NEDA-3 is defined as no new/enlarging T2 lesions compared to Month 6 on any MRI scan (scheduled or unscheduled) after Month 6
- An analysis using the mFAS in which the clinical disability progression-free component of NEDA-3 is based on 6-month clinical disability progression-free

For each of the supplemental analyses described above the number and percentage of participants achieving NEDA-3 in Months 6 to 18 will be presented. The 2-sided 95% CI for the proportion of participants achieving NEDA-3 in Months 6 to 18 will be calculated using an exact method ([Clopper and Pearson, 1934](#)).

## 2.6 Analysis supporting secondary objectives

Analysis of efficacy endpoints supporting secondary objectives is described in [Section 2.6.1](#) – [Section 2.6.6](#) below.

Analysis of safety and PRO endpoints supporting secondary objectives is described in [Section 2.7](#) and [Section 2.10](#), respectively.

### 2.6.1 Secondary endpoint(s)

Secondary efficacy endpoints include the following:

- Number of confirmed relapses in Months 6 to 18
- 3-month disability worsening-free in Months 6 to 18 (yes/no)
- NEDA clinical (relapse-free, 3-month clinical disability progression-free) in Months 6 to 18 (yes/no)
- NEDA radiological (MRI activity-free) in Months 6 to 18 (yes/no) for ofatumumab-treated participants, where MRI activity-free is defined as no Gd+ lesions on any MRI scan (scheduled or unscheduled) after Month 6, or new/enlarging T2 lesions compared to Month 6 on any MRI scan (scheduled or unscheduled) after Month 6
- NEDA radiological (MRI activity-free) in Months 6 to 18 (yes/no) for ofatumumab-treated and healthy control participants, where MRI activity-free is defined as no new/enlarging T2 lesions compared to Month 6 on any MRI scan (scheduled or unscheduled) after Month 6
- Change from baseline, as well as change from Month 6 re-baseline, in the following conventional MRI metrics by time point: Gd+ lesion number, Gd+ lesion volume, T2 lesion volume and T1 unenhancing lesion volume
- Values of the following conventional MRI metrics by time point (baseline or post-baseline, as appropriate): new Gd+ lesion number, T2 lesion number, new/enlarging T2 lesion number, new unenhancing T1 lesion number and new/enlarging T2 lesion volume

- Percent change from baseline and percent change from Month 6 re-baseline in brain volume parameters (whole brain and regional) by time point (also obtained in healthy control participants for normalization purposes)

Note that Gd will not be given to healthy control participants and Gd enhanced T1 MRI imaging will not be conducted in healthy control participants.

## 2.6.2 Statistical hypothesis, model, and method of analysis

Values, changes from baseline and percent changes from baseline (brain volume parameters only) in the following endpoints will be summarized by Cohort and time point with descriptive statistics using the FAS or HCAS, as appropriate:

- Conventional MRI metrics including Gd+ lesion number, Gd+ lesion volume, T2 lesion volume and T1 unenhancing lesion volume
- Brain volume parameters (whole brain and regional)

In addition, changes and percent changes (for applicable endpoints) from Month 6 re-baseline to post-Month 6 time points will be summarized in a similar fashion.

Percent change from Month 6 re-baseline to post-Month 6 time points in brain volume parameters will be calculated via the following steps:

1. Calculate normalized brain volume (NBV) at post-baseline time points as follows (note that NBV at baseline and percentage brain volume change [PBVC] at post-baseline time points are provided by the MRI vendor):  
NBV at post-baseline time point = [(PBVC at post-baseline time point/100) x NBV at baseline] + (NBV at baseline)
2. Calculate the percent change from Month 6 re-baseline to post-Month 6 time points using the NBVs at Month 6 re-baseline and Months 12, 18 and 30 from Step 1 according to the formula provided in [Section 2.1.1](#).

Values of the following endpoints will be summarized by Cohort and time point (baseline or post-baseline, as appropriate) with descriptive statistics using the FAS or HCAS, as appropriate:

- Conventional MRI metrics including new Gd+ lesion number, T2 lesion number, new/enlarging T2 lesion number, new unenhancing T1 lesion number and new/enlarging T2 lesion volume

The annualized new/enlarging T2 lesion rate will be calculated using a participant-based approach and a cohort-based approach as follows:

- Participant-based approach: [(number of new/enlarging T2 lesions in Months 6 to 18 for a given participant) / (number of days in Months 6 to 18 for a given participant)] × 365.25
- Cohort-based approach: [(total number of new/enlarging T2 lesions in Months 6 to 18 for all participants within a cohort) / (total number of days in Months 6 to 18 for all participants within a cohort)] × 365.25

The number of new/enlarging T2 lesions in Months 6 to 18 for each participant = Month 12 value (i.e., Month 12 scan relative to Month 6 scan) + Month 18 value (i.e., Month 18 scan relative to Month 12 scan). Participants are excluded from this calculation if the Month 6 value

(i.e., Month 6 scan relative to baseline scan) is missing. Only participants with a Month 6 value and at least one of the Month 12 or Month 18 values are included in this calculation.

The annualized new/enlarging T2 lesion rate (participant-based) will be summarized descriptively as a continuous variable by Cohort using the FAS or HCAS, as appropriate. The annualized new/enlarging T2 lesion rate (cohort-based), along with its components (i.e., numerator and denominator), will be reported by Cohort using the FAS or HCAS, as appropriate.

The annualized relapse rate (ARR) will be calculated using a participant-based approach and a cohort-based approach as follows:

- **Participant-based approach:**  $[(\text{number of confirmed relapses in Months 6 to 18 for a given ofatumumab-treated participant}) / (\text{number of days in Months 6 to 18 for a given ofatumumab-treated participant})] \times 365.25$
- **Cohort-based approach:**  $[(\text{total number of confirmed relapses in Months 6 to 18 for all participants within the ofatumumab-treated cohort}) / (\text{total number of days in Months 6 to 18 for all participants within the ofatumumab-treated cohort})] \times 365.25$

The ARR (participant-based) will be summarized descriptively as a continuous variable using the FAS. The ARR (cohort-based), along with its components (i.e., numerator and denominator), will be reported using the FAS. The ARR (both participant- and cohort-based) will also be derived through Month 18 and summarized descriptively using the FAS.

The number and percentage of participants with 0, 1, 2 or  $\geq 3$  confirmed relapses in Months 6 to 18 will be presented using the FAS. In addition, the number and percentage of participants with at least 1 confirmed relapse in Months 6 to 18 will be presented using the FAS. Participants with confirmed relapses through Month 18 will be summarized in a similar manner using the FAS.

The number and percentage of participants achieving 3-month disability worsening-free in Months 6 to 18 will be presented using an observed case approach (completers) using the FAS. The number and percentage of participants achieving NEDA clinical in Months 6 to 18 and NEDA radiological in Months 6 to 18 using the ofatumumab-treated participants derivation described in [Section 2.6.1](#) will be presented using the mFAS. In addition, the number and percentage of participants achieving NEDA radiological in Months 6 to 18 using the ofatumumab-treated and healthy control participants derivation described in [Section 2.6.1](#) will be presented using the mFAS or HCAS, as appropriate. The 2-sided 95% CI for the proportion of participants achieving each of these endpoints will be calculated using an exact method ([Clopper and Pearson, 1934](#)).

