The proposed study would provide rigorous clinical, MRI, digital and biomarker data demonstrating the effect of ofatumumab in a naïve RRMS population at first diagnosis and would provide the first data relative to healthy controls, identified data gaps in the US. The very early MS young adult population in this study will consist of treatment naïve RRMS patients that are within 6 months of diagnosis at the time of study entry. Detailed data will be collected within the first month to document a rapid response to therapy. Further, a HC group will be used to analyze select endpoints vs ofatumumab (e.g., brain atrophy) with the strategy of showing normalization of brain structural/functional changes. This would also highlight the need for high efficacy therapy very early in the course of the disease as the extension data of up to 30 months would potentially show stabilization long term.

2 Objectives, endpoints and estimands

Table 2-1 Objectives and related endpoints

[figure not shown]
Objective(s)	Endpoint(s)

Primary Objective(s)
 
 The primary objective is to explore the impact of ofatumumab (OMB) on the ability to achieve No Evidence of Disease Activity (NEDA-3) status in treatment-naïve, very early RRMS patients over an 18 month, open-label study period after a re-baseline of MRI at 6 months 	
Endpoint(s) for primary objective(s)
 
 NEDA-3 (Relapse-free, 3-month clinical disability progression-free, MRI activity-free) in Months 6 to 18 (yes/no)

Secondary Objective(s)
 
Evaluate the effect of ofatumumab on various clinical (NEDA, disability, relapse) metrics at 18 months
	
Endpoint(s) for secondary objective(s)
 
Baseline and months 6, 12, 18, 30 (T1 Gd)

 Evaluate the effect of ofatumumab on conventional MRI metrics, with MRIs at 	

- Number of relapses
- 3-month Disability Worsening-free (yes/no)
- NEDA clinical in Months 6 to 18 (yes/no)
- NEDA radiological in Months 6 to 18 (yes/no)
- Change from Baseline in Conventional MRI metrics
(Gd+ lesion number, new Gd+ lesion number, Gd+ lesion volume, T2 lesion

Objective(s)	Endpoint(s)
@ Baseline, month 6, 18 and T1/T2 @ every timepoint)	number (Baseline), New/enlarging T2 lesion number (post-Baseline), T2 lesion volume, new unenhancing T1 lesion number, T1 unenhancing lesion volume)

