4.1 Rationale for study design

This study is an open-label, multi-center, prospective eighteen-month study in a minimum of 118 MS patients with early RRMS (defined as within 6 months of diagnosis of clinically definite RRMS) and who are DMT treatment naïve. RMS patients will be benchmarked against age- and sex-matched healthy controls (n=50) for select secondary [REDACTED]. The concept herein will expand on previous ofatumumab studies and provide important clinical and safety data in an earlier RRMS population than studied in ASCLEPIOS I and II. Further, this study will investigate multiple secondary [REDACTED] (over the course of up to 30 months; all patients are in trial for 18 months, but the optional extension period extends to 30 months) to build the data sets on early use of ofatumumab using MRI metrics, patient reported outcomes (PRO), biomarker and digital monitoring technologies. Finally, the study will compare select endpoints vs age- and sex-matched HC patients to provide first evidence of safety and disease stabilization measured by MRI/[REDACTED] vs non-MS patients.

Due to the limited time from diagnosis and lack of experience with B cell depleting therapies that this population will have, an open-label, multi-center design was selected to facilitate recruitment. Further, the clinical trial space is very active with numerous therapies under development and therefore careful consideration was taken regarding impact on the patient when designing monitoring outcomes. The design limited the number of clinic visits and MRIs to minimum acceptable levels and focused on using “at home” digital technology for monitoring when available.

Finally, the use of a HC group for comparison is novel in the clinical trial program for ofatumumab. In the Phase 2 APOLITOS trial, a Japanese/Russian population was studied to evaluate the efficacy and safety of ofatumumab versus placebo in RMS patients. Although this study included RMS placebo-treated patients, no study has compared ofatumumab treated patients to non-MS HCs. The HC comparator data can provide important information on safety outcomes (e.g., infections) and the ability of ofatumumab to normalize CNS pathology as measured by MRI and [REDACTED] of disease.

Rationale of chosen endpoints:

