12.5 Analysis supporting secondary objectives

12.5.1 Efficacy endpoint(s)

For all efficacy analyses, the FAS will be used. The healthy control set will be used if applicable.

Descriptive statistics will be provided for the following variables:

- Number of relapses during the study
- 3-month disability worsening-free (yes/no) during the study
- NEDA clinical in Months 6 to 18 (yes/no)
- NEDA radiological in Months 6 to 18 (yes/no)
- Change from Baseline in conventional MRI metrics (Gd+ lesion number, new Gd+ lesion number, Gd+ lesion volume, T2 lesion number (Baseline), New/enlarging T2 lesion number (post-Baseline), T2 lesion volume, new unenhancing T1 lesion number, T1 unenhancing lesion volume) by visit/time
- Brain volume loss (BVL) assessment (whole brain and regional) (also obtained in HC for normalization purpose) by visit/time

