**Table 1 Study objectives and endpoints**

Objective(s)	Endpoint(s)

Primary Objective(s)
 
 
The primary objective is to explore the impact of ofatumumab on the ability to achieve No Evidence of Disease Activity (NEDA-3) status in treatment-naïve, very early RRMS participants over an 18 month, open-label study period after a re-baseline of MRI at 6 months
 
	
Endpoint(s) for primary objective(s)
 
 
NEDA-3 (relapse-free, 3-month clinical disability progression-free, MRI activity-free) in Months 6 to 18 (yes/no)
 

Secondary Objective(s)
 
 
Evaluate the effect of ofatumumab on various clinical (NEDA, disability, relapse) metrics at 18 months
 
Evaluate the effect of ofatumumab on conventional MRI metrics, with MRIs at Baseline and Months 6, 12, 18, 30 (T1 gadolinium (Gd) @ Baseline, Month 6, 18 and T1/T2 @ every timepoint)
 
Evaluate the effect of ofatumumab on patient reported outcomes (PROs) (Quality of Life in Neurological Disorders [NeuroQOLTM], Patient Determined Disease Steps [PDDS])
 
Evaluate the effect of ofatumumab vs healthy controls on 1) whole brain and regional atrophy measured at Month 18/30 after re-baseline at 6 months; and 2) regional atrophy measured 18/30 months from Baseline
 
Evaluate the safety and tolerability of ofatumumab
 
	
Endpoint(s) for secondary objective(s)
 
 
Number of confirmed relapses in Months 6 to 18
 
3-month disability worsening-free in Months 6 to 18 (yes/no)
 
NEDA clinical in Months 6 to 18 (yes/no)
 
NEDA radiological in Months 6 to 18 (yes/no)
 
Change from baseline in conventional MRI metrics (Gd+ lesion number, new Gd+ lesion number, Gd+ lesion volume, T2 lesion number (Baseline), new/enlarging T2 lesion number (post-Baseline), T2 lesion volume, new/enlarging T2 lesion volume, new unenhancing T1 lesion number, T1 unenhancing lesion volume)
 
Change from baseline in PROs (NeuroQOLTM, PDDS) (also obtained in healthy controls)
 
Brain volume assessment (whole brain and regional) (also obtained in healthy controls)
 
Adverse events, laboratory data, physical examination, and vital signs (also obtained in healthy controls)
 

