## 2 Statistical methods

### 2.1 Data analysis general information

The statistical analysis outlined in this SAP will be performed by United BioSource LLC (UBC), a Novartis-designated Contract Research Organization (CRO), using SAS® version 9.4 or higher.

The primary analysis will be based on Month 18 data, i.e., all data up to and including Month 18. This analysis will be performed after all participants have completed their Month 18 visit, discontinued study treatment prior to Month 18 (ofatumumab-treated participants) or discontinued the study prior to Month 18 (healthy control participants) (see [Section 2.1.1](#) and [Section 2.13](#) for additional details). The final analysis will include all data through Month 30.

For continuous variables, descriptive statistics will include number of participants (n) with available data, mean, standard deviation, minimum, maximum, median and 25th and 75th percentiles. For categorical variables, frequency counts and percentages will be reported. Where appropriate, 2-sided 95% confidence intervals (CIs) for point estimates of the mean or proportion will be provided.

In general, data summaries will be presented for ofatumumab-treated participants in the relevant analysis set. In instances where data are collected for both ofatumumab-treated participants and healthy control participants, data summaries will be presented **by Cohort** (ofatumumab-treated participants or healthy control participants) and on all participants in the respective analysis set.

All data (collected or derived) will be listed appropriately.

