#### 5.4.2 Analysis supporting secondary objective(s)

There is no hypothesis testing planned for the analyses supporting the secondary objectives of this study.

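### The atrophy objective compares ofatumumab with healthy controls but no between-cohort difference is planned; separately, the by-cohort T2-based NEDA radiological result uses unlike inclusion rules

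*SAP*

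**What the plan says.** **Atrophy.** SAP Table 1 (as Protocol Table 2-1) states the objective in two parts: "Evaluate the effect of ofatumumab vs healthy controls on 1) whole brain and regional atrophy" after the Month 6 re-baseline, and "regional atrophy measured 18/30 months from Baseline". Protocol 4.1 adds that "the study will compare select endpoints vs age- and sex-matched HC patients". For the analysis, Protocol 12.5.1 says "Descriptive statistics will be provided for the following variables", and brain volume is on that list. SAP 2.6.2 follows: values and percent changes "will be summarized by Cohort and time point with descriptive statistics using the FAS or HCAS, as appropriate". SAP 2.1 adds that, where appropriate, "2-sided 95% confidence intervals (CIs) for point estimates of the mean or proportion will be provided". SAP 5.4.2 states that "There is no hypothesis testing planned for the analyses supporting the secondary objectives of this study", and SAP 2.13 excludes testing and estimation at Month 30.

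**T2-based NEDA radiological.** SAP 2.6.1 gives one definition for both cohorts: no new or enlarging T2 lesion, relative to Month 6, on any later scan. SAP 2.6.2 reports it on the mFAS for patients and the HCAS for controls. SAP 2.2 defines those sets, and SAP 2.6.3 and 2.6.4 carry the NEDA-3 handling rules of 2.5.3 and 2.5.4 over to this endpoint.

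**The concern.** Protocol 1.2 gives showing normalization of brain changes as the strategy behind the control group. Two columns of means do not show how large a difference remains compatible with the data, and similar means may be read as normalization. Age and sex are collected and used to match the cohorts, but no visible analysis uses them.

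For the T2-based result, two percentages will be shown by cohort under one definition. If participants enter the two denominators by different rules, part of any gap between them reflects the rules rather than lesions. The control percentage also depends on a missing-scan rule that the SAP does not state.

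**Working it through.** **The plan's own figures.** Inputs from SAP 3.1: 100 evaluable patients, expected NEDA-3 of 80% or 85%, 15% drop-out.
- 1.96 × √(0.80 × 0.20 / 100) = 7.8%
- 1.96 × √(0.85 × 0.15 / 100) = 7.0%
- 100 / (1 − 0.15) = 117.6, so 118

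All reproduce. They concern patients only. SAP 3.2 gives 50 controls with no SD, precision or drop-out rate.

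**Part 1: precision of the missing contrast.** Assume independent cohorts with a common SD. The 95% half-width of the difference in means is 1.96 × SD × √(1/n₁ + 1/n₂).
- 100 vs 50: 1.96 × √0.0300 = 0.34 SD
- 100 vs 42: 1.96 × √0.0338 = 0.36 SD (assumes the patients' 15% drop-out in controls: 7.5, rounded to 8)

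Without an SD these cannot be turned into percent brain volume. Any shift from adjusting for age and sex is unknown, and may be small given the matching and the 18–35 age range.

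**Part 2: who enters each denominator** (SAP 2.2, 2.5.3, 2.5.4).

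| Situation | Patients (mFAS) | Controls (HCAS) |
|---|---|---|
| Stopped for lack of efficacy or death | Kept, non-response | No corresponding rule |
| Otherwise incomplete, activity seen | Kept | Kept |
| Otherwise incomplete, no activity seen | Dropped | Kept; effect of a missing scan not stated |
| All scans done, a relapse or EDSS assessment missed, no activity | Dropped | Kept |

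The only missing-scan rule for this endpoint is exclusion from the mFAS, which cannot apply to a control. The non-response imputation in SAP 2.5.6 and 5.1.3.3 covers only NEDA-3 after a dose of ofatumumab. By contrast, the annualized T2 rate in SAP 2.6.2 has one rule for both cohorts: a Month 6 value and at least one of the Month 12 or Month 18 values.

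**Part 2: an ambiguity.** SAP 2.5.3 makes retained incomplete patients with disease activity non-responders for NEDA-3 and its associated endpoints, and counts relapse and EDSS progression as activity. Imported through 2.6.3, that could fail a patient with no new T2 lesion, against 2.6.1. It could equally be read as meaning MRI activity only.

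**Part 2: size in patients.** Drop-outs: 15% of 118 ≈ 18. The annualized relapse rate in Protocol 1.1 is 0.10–0.11, from an older population. Expected relapses = 18 × years at risk after Month 6 × rate.
- Half a year (assumed): 18 × 0.5 × 0.10 = 0.90, to 18 × 0.5 × 0.11 = 0.99
- Drop-out uniform over 18 months (assumed; mean 2/3 × 0.5 = 0.33 year): about 0.6–0.7
- One full year for all, an upper extreme: 18 × 1.0 × 0.11 = 1.98

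Relapses with a new T2 lesion would not matter; EDSS-only cases and completers with a missed assessment would add some. If 98 of 100 complete patients are T2-free (assumed), one or two extra failures give 98/101 = 97.0% or 98/102 = 96.1%, against 98.0%.

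**Part 2: size in controls.** Suppose 8 of 50 lack scans and the rest are lesion-free (both assumed). Leaving them out gives 42/42 = 100% (exact 95% CI 91.6–100). Counting them as failures gives 42/50 = 84% (70.9–92.8). With 4 unscanned: 46/46 = 100% (92.3–100) or 46/50 = 92% (80.8–97.8). With none missing, both give 50/50 = 100%.

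**The case against.** The study benchmarks patients against controls, and both documents plan description, so comparing need not mean a modelled contrast. The cohorts are already matched on age and sex. SAP 2.1 provides n, mean and SD, from which a reader can compute both the crude difference and its unadjusted interval. This stands, and it limits the harm: what is missing is a reported contrast and an adjusted one. A reader might infer that the SAP departs from the protocol or owes a hypothesis test. The documents support neither: Protocol 12.5.1 is descriptive too, and SAP 5.4.2 rules out testing. Neither that section nor SAP 2.13, which bars estimation only at Month 30, prevents an interval at Month 18.

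On the T2 result, the explicit objective against controls is atrophy. T2 lesion counts and the annualized T2 rate are already shown by cohort on the FAS and HCAS. The patient-side effect is small, and the control-side range rests on an assumed number of missing scans. All of that stands too. A reader might infer that the SAP plainly counts a relapse as a radiological failure, or that the mFAS keeps incomplete patients only when they showed activity. The first is one of two readings. The second overlooks those who stopped for lack of efficacy or death, who are also kept. Nor does any text say that unscanned controls count as failures. What survives is that the denominator rules differ under either reading and that controls have no applicable missing-scan rule. Redaction does not explain this, because the opening of SAP 2.6 places these analyses in 2.6.1 to 2.6.6, which are visible.

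**Conclusion.** Two separate points hold, both on secondary endpoints and both limited to the visible text.

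1. **Atrophy:** an inexpensive improvement, not an error. A comparative objective is answered only by cohort summaries. The unadjusted interval would be about ±0.34 SD with 100 and 50 evaluable, assuming a common SD that the documents do not give.
2. **T2-based NEDA radiological:** the inclusion rules are unlike in the two cohorts, and the failure rule for incomplete patients is ambiguous. The effect on the patient percentage is probably small, one or two points under the assumptions shown. In controls it is nil if no scans are missing and otherwise depends on an unstated rule; the documents give no control drop-out rate.

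Neither point touches the primary endpoint.

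**What to change.** **Atrophy (SAP 2.6.2).** At Month 18, report the ofatumumab-minus-control difference with a 95% CI for percent change from Month 6 (whole brain and regional) and for regional percent change from Baseline. Give it unadjusted and from a linear model with cohort, age and sex. This is estimation only, with no test; Month 30 stays descriptive. Cost: SAP wording and one model per parameter and period, from data already collected. Downsides: extra output, several intervals without multiplicity adjustment, reliance on a linear model, and residual confounding because the cohorts are not randomized.

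**T2-based result (SAP 2.6.2 to 2.6.4).** For the by-cohort row, apply the annualized T2 rate's scan rule to both cohorts. Count only new or enlarging T2 lesions relative to Month 6 as failure, and report the number excluded per cohort. Keep the mFAS composite result for patients alongside. State in 2.6.3 that relapse or EDSS progression alone is not radiological non-response for this row. Cost: a few sentences and one table row. Downsides: the harmonised row does not count stopping for lack of efficacy or death as failure, which can favour ofatumumab (with 2 such patients, assumed, 98/100 = 98.0% instead of 98/102 = 96.1%); the retained mFAS result discloses this. A participant with only one later scan can also count as lesion-free.

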## 2.2 Analysis sets

The Full Analysis Set (FAS) will include all enrolled participants that received any study drug.

The Safety Analysis Set (SAF) will be the same as the FAS.

The Healthy Control Analysis Set (HCAS) will include all enrolled healthy control participants. This analysis set will be used in the analysis of data collected from healthy control participants.

The modified FAS (mFAS) will include all participants in the FAS except for those who discontinued treatment prematurely prior to Month 18 for reasons other than lack of efficacy or death, or those who completed their Month 18 visit but missed relapse/EDSS/MRI (Gd+ or

new/enlarging T2 lesions) at Month 6, 12 or 18, unless they showed disease activity (i.e., MRI activity after Month 6 through 18 or relapse/3-month clinical disability progression between Months 6 and 18). The mFAS will be used for NEDA-3, NEDA clinical and NEDA radiological efficacy analyses.

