### **2.6.3 Handling of intercurrent events**

For NEDA clinical in Months 6 to 18 and NEDA radiological in Months 6 to 18, the same approach outlined for NEDA-3 in [Section 2.5.3](#) will be followed. For all other secondary endpoints, there is no imputation of missing data planned for this study.

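### The Months 6 to 18 T2 lesion rate admits participants on a Month 6 reading against baseline that the rate never uses; the condition should be an evaluable Month 6 scan

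*SAP*

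**What the plan says.** SAP 2.6.2 builds each participant's Months 6 to 18 lesion count from two readings: "Month 12 value (i.e., Month 12 scan relative to Month 6 scan") plus "Month 18 value (i.e., Month 18 scan relative to Month 12 scan"). In the participant-based rate the count is divided by the "number of days in Months 6 to 18 for a given participant" and scaled to 365.25 days. The cohort-based rate sums the same quantities over participants.

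The entry rule follows: "Participants are excluded from this calculation if the Month 6 value" ("i.e., Month 6 scan relative to baseline scan) is missing"). The next sentence repeats it in positive form: "Only participants with a Month 6 value and at least one of the Month 12 or Month 18 values are included in this calculation".

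For this kind of endpoint SAP 2.6.3 adds: "For all other secondary endpoints, there is no imputation of missing data planned for this study". Nothing restores a participant whom the entry rule removes. The SAP gives no reason for requiring the reading against baseline.

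**The concern.** The rate is anchored at Month 6, in line with the re-baselining of MRI described in Protocol section 3 and SAP 1.1. It needs the Month 6 scan as the reference for the Month 12 comparison. It does not need to know how many lesions appeared between baseline and Month 6. Because the SAP spells out what it means by the Month 6 value, a programmer would test the baseline-referenced variable and not the presence of a Month 6 scan.

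Someone whose baseline scan was unusable, but whose Month 6, 12 and 18 scans were all good, would then be left out although the whole count is observed. The same rule admits someone with only one of the two interval readings, so it can accept half the window and reject all of it. At stake are a few participants in one descriptive summary, in either cohort.

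**Working it through.** The documents state no figure for this rate, so there is none to reproduce. The check is logical, followed by a rough size.

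**Step 1. Which scans each reading needs.** From SAP 2.6.2, assuming that a reading exists when both of its scans are usable:
- Month 6 value: baseline and Month 6 scans
- Month 12 value: Month 6 and Month 12 scans
- Month 18 value: Month 12 and Month 18 scans

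**Step 2. The two rules.**
- SAP rule: Month 6 value present, and Month 12 or Month 18 value present.
- Alternative: Month 6 scan usable, and Month 12 or Month 18 value present.

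**Step 3. Compare over all patterns.** Four scans, each usable or not, give 2 × 2 × 2 × 2 = 16 patterns. With a usable baseline scan (8 patterns) the rules always agree. Without one (8 patterns) they differ in two. The rows that matter:

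| Baseline | M6 | M12 | M18 | Months 6–18 count | SAP rule | Alternative |
|---|---|---|---|---|---|---|
| no | yes | yes | yes | complete | out | in |
| no | yes | yes | no | first half only | out | in |
| yes | yes | yes | no | first half only | in | in |
| yes or no | no | yes | yes | second half only | out | out |

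The first two rows are the only differences. The second and third have identical Months 6 to 18 data but are treated differently because of the baseline scan. In the last row the Month 6 scan is missing, so the Month 12 reading cannot exist, and both rules exclude the participant.

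**Step 4. Size.** The affected share q is not in the documents; 0% to 3% is assumed. SAP 3.1 plans 100 patients after 15% dropout (100 / 0.85 = 117.6, enrolled as 118). The 100 is the better base, because anyone without the later scans is out under either rule. SAP 3.2 plans 50 controls.
- Patients: 0 × 100 = 0 to 0.03 × 100 = 3.
- Controls: 0 × 50 = 0 to 0.03 × 50 = 1.5, so at most 2.
- Standard error inflation from losing a share q, 1/√(1 − q) − 1: 0% at q = 0, and 1/√0.97 − 1 = 1.5% at q = 3%.

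**The case against.** The strongest reply is that the case will hardly arise. Protocol Table 8-1 schedules a screening MRI for both cohorts. Protocol 5.1 requires the ability to obtain MRI and excludes controls whose screening scan is abnormal. Protocol 8.3.6 has each scan checked centrally and asks for a repeat of a defective one. SAP 2.1.1 takes the last non-missing assessment up to first dose or Week 0 as baseline, unscheduled ones included. All of this stands and makes the case uncommon. It does not make it impossible: under SAP Table 6 a repeat after Study Day 1 cannot serve as baseline.

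A second reply is that little is lost. This also stands. SAP 2.6.2 still summarises the same participant's Month 12 and Month 18 lesion numbers by time point, and SAP 5.4.2 plans no hypothesis test.

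A third is that the rule does useful work by confirming that a Month 6 reference exists. That is right when the Month 6 scan itself is missing, but a condition on the scan does the same work without the side effect.

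A reader might go further and infer that the primary analysis has the same fault, because SAP 2.2 removes from the mFAS Month 18 completers who missed MRI (Gd+ or "new/enlarging T2 lesions) at Month 6, 12 or 18, unless they showed disease activity". The documents do not support that. Neither 2.2 nor the matching text in 2.5.3 and 2.5.4 mentions baseline; the plain sense is that the assessment was missed at that visit. Reading the 2.6.2 definition into those sections carries a parenthesis from one calculation into another. SAP 2.5.1 judges T2 activity against Month 6, and the completer analysis in 2.5.6 asks for completed Month 6 and Month 18 visits, not for a reading against baseline.

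**Conclusion.** The entry condition in SAP 2.6.2 names the wrong reading for a rate anchored at Month 6. It drops usable data only when the Month 6 and Month 12 scans are evaluable and the Month 6 reading against baseline is not available: 2 of 16 scan patterns. It would be too strong to say that the plan discards valid data in general. In the other patterns the rule gives the same result as a condition on the Month 6 scan.

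Under the assumed 0% to 3%, the loss is 0 to 3 of about 100 patients and 0 to 2 of 50 controls, with at most about 1.5% on the standard error. No direction of bias is shown. This is a minor wording fault in a descriptive summary, worth correcting because the correction changes nothing for anyone with a usable Month 6 reading against baseline.

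**What to change.** In SAP 2.6.2, replace the two sentences on the Month 6 value with:

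> Participants are included if the Month 6 scan was evaluable as the reference scan and a Month 12 value, a Month 18 value, or both are available.

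An available Month 12 value already shows that the Month 6 scan could serve as the reference, so the new term needs no elaborate definition. If the reading against baseline is required on purpose, keep the rule and state why.

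Leave the mFAS rule as it is. At most, add a line confirming that a missed Month 6 MRI in 2.2, 2.5.3 and 2.5.4 means a scan that is absent or not evaluable, not an absent reading against baseline.

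The cost is SAP wording and one changed condition in the derivation of the rate. No new data are needed.
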